**Table 8: Scheduled TCAC visits**

		Month 1	Month 2	Month 3	Month 4	Month 5	Month 6
Routine Health Screening	RK003	X	X	X	X	X	X
TCAC Transition	TR001	[X]	[X]	[X]	[X]	[X]	[X]

X required CRF, [X] may be required if updated or as necessary

## 5.3 Database management

### 5.3.1 Structure of the database

This study will rely on two databases. One will be used to capture participant characteristics and outcomes (main database). The other database will be a study administrative database used for monitoring of corrections release and communication with participants following release (administrative database). Main study data will be captured into a secure web based REDCap™ (Research Electronic Data Capture) electronic database. The Redcap database provides; an intuitive interface for validated data entry; audit trails for tracking data manipulation and export procedures; automated export procedures for seamless data downloads to common statistical packages; and procedures for importing data from external sources. The administrative database will be developed within Microsoft Access. This database will have an Access frontend connected to a SQL-based server to allow for simultaneous access and data-entry from multiple sites. We will develop a separate database form within REDCap for each paper case report form (CRF). All fields will have appropriate range-checks for validation during data-entry. Field numbers and names in the database will correspond to numbers and names on the CRF. Trained data capturers or research assistants will manually input all data into the electronic database from the paper CRFs.

Data entry for the release and communication database will be maintained on a daily basis for real-time use of data. On the day of enrolment, the identification and contact details will be entered into the release and communication database. The release database will be updated

within seven days of the participant's expected release using either participant self-reported information or confirmed DCS release dates. Data entry validation and automatic range checks will be incorporated in most data fields to reduce data entry errors. In addition, a data monitor will compare approximately 10% of CRFs with data within the database. This will help to identify systematic errors. Such problems may lead to a review of a larger proportion of CRFs. In addition, bi-weekly electronic checks for inconsistencies within and across forms will be performed followed by CRF review of any data queries that are generated.

### 5.3.2 Database access

Access to the database (data entry, reporting, and extraction) is controlled by the Data Manager, Study Manager, and the REDCap Database Administrator. Study personnel requiring access to the database must complete required documentation and training prior to receiving the necessary username and password.

### 5.3.3 Locking of final database

The final study database is locked to changes after the clean file form has been signed. Final storage of the database is with the production folder structure together with all the Metadata, source data and the user written programs and the version of the system used to produce the database. The folder is given a special icon to show it is locked and the available choices are restricted to reading the data.

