#### 2.4.2 Randomization

We will perform individual randomization blocked by correctional facility. Study staff will open numbered envelopes with the allocation following enrollment. Participants will be randomized 1:2 to either the standard of care or the TCAC using sequential envelopes with study arm determination sealed inside (blocked by study site and based on random number generation). Participants and members of the research team recruiting and implementing the strategy will be unmasked to randomization assignment due to the behavioral nature of the strategy and need for team members to explain the study arm procedures to participants. Study assignments will be masked to staff performing outcome assessments and the investigators until all outcome data have been collected.

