## 2.7.3 Care verification

Clinical records will be accessed to determine linkage to care status, timing of linkage to care, ART continuation, retention in care, and HIV RNA results. This will be done through reviewing paper clinic charts, electronic clinic data (tier.net), and electronic laboratory data (NHLs Trackcare system). Linkage between participants and records will be based on matching surname, first name, date of birth, sex, and appropriate date range.

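### Masking may end (section 2.4.2) before the database is locked (section 5.3.3), so final cleaning and outcome classification could be done with the arms known

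*Combined protocol and SAP*

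**What the plan says.** Section 2.4.2 sets how long masking lasts: "Study assignments will be masked to staff performing outcome assessments and the investigators until all outcome data have been collected". The same section accepts that others know the arm throughout: "Participants and members of the research team recruiting and implementing the strategy will be unmasked to randomization assignment".

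Section 5.3.3 sets when the data become final: "The final study database is locked to changes after the clean file form has been signed". It does not mention allocation or masking.

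Section 5.3.1 describes cleaning: "bi-weekly electronic checks for inconsistencies within and across forms will be performed followed by CRF review of any data queries that are generated". It also provides for a data monitor to compare about 10% of CRFs with the database, with a wider review if problems appear, and for audit trails in REDCap. On data entry it says: "Trained data capturers or research assistants will manually input all data into the electronic database from the paper CRFs". Section 5.3.2 governs access by role: "Access to the database (data entry, reporting, and extraction) is controlled by the Data Manager, Study Manager, and the REDCap Database Administrator". Neither section sets a masking condition.

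Section 2.7.3 explains how participants are tied to clinic and laboratory records: "Linkage between participants and records will be based on matching surname, first name, date of birth, sex, and appropriate date range".

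Section 2.9.2 defines the primary outcome by a rule on visit dates (two HIV care visits 90 days apart, the last at 5 to 7 months). It analyses all randomized individuals and adds a second analysis that removes participants for late release, re-incarceration, death or withdrawal.

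**The concern.** In a trial where participants and implementing staff know the arm, masked assessment is one of the few protections for the outcome data, and section 2.4.2 shows that the sponsor wanted it. That protection is tied to the end of collection rather than to the point at which the data can no longer change.

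Three kinds of decision can fall between those two points: how a late query on a visit date is resolved, whether an uncertain record match is reopened, and whether a participant counts as in care or as excluded from the follow-up analysis. Each can change a participant's status. If the person deciding knows the arm, the decision can lean one way without anyone intending it. The comparison of arms is a listed primary objective (section 1.2), and the Study Summary says the pilot should yield a protocol and manual ready for a full trial, so the gap could be carried forward.

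**Working it through.** **Order of events**

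1. Masking of outcome assessors and investigators need last only until outcome collection ends (2.4.2).
2. The lock follows signature of the clean file form (5.3.3).
3. A file cannot be declared clean before its data have arrived, so step 2 comes after step 1. This order is inferred from the two sections; the plan does not state it.
4. No section extends masking from step 1 to step 2, requires lock before allocation is revealed, or says that query resolution or outcome derivation is masked.

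**What falls in the interval**

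| Task | Section | Exposed? |
|---|---|---|
| First-pass record matching | 2.7.3 | No, on a plain reading: it is how outcome data are collected |
| Re-matching during cleaning | 2.7.3, 5.3.1 | Yes, if it occurs |
| Queries raised during follow-up | 5.3.1 | No: checked every two weeks |
| Last queries and any widened CRF review | 5.3.1 | Yes |
| Classifying the outcome and the four exclusions | 2.9.2 | Yes, if done after collection |

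The plan does not define when outcome data count as collected. If it means the last participant contact, more matching is exposed. If it means the end of abstraction and query-driven review, little is.

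**Weight of one participant**

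Inputs: 60 care-as-usual and 120 TCAC (4.1, Table 4), and 78% ascertainment (text under Table 4).

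The plan attaches no figure to this point. Its power statement does confirm how these inputs are used. Numbers analysed are 0.78 × 60 = 46.8 and 0.78 × 120 = 93.6. With 0.25 versus 0.49, two-sided alpha 0.05 and a pooled-variance normal approximation:

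- pooled proportion = (46.8 × 0.25 + 93.6 × 0.49) / 140.4 = 0.41
- null SE = √[0.41 × 0.59 × (1/46.8 + 1/93.6)] = 0.0881
- alternative SE = √[0.25 × 0.75/46.8 + 0.49 × 0.51/93.6] = 0.0817
- power = Φ[(0.24 − 1.96 × 0.0881)/0.0817] = 79.5%, against the stated 80%

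The share of an arm held by one participant is 1/n:

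| Basis | Care as usual | TCAC |
|---|---|---|
| Full arms (60, 120) | 1/60 = 1.7 points | 1/120 = 0.8 points |
| 78% ascertained (47, 94) | 1/47 = 2.1 points | 1/94 = 1.1 points |

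The first row is closer to the all-randomized analysis in 2.9.2. Because 4.1 counts released inmates, the number randomized may exceed 180, and each share would then be slightly smaller.

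**The case against.** The strongest reply is that section 2.4.2 sets how long masking must last and does not schedule an unmasking. A reader might infer that the arms will be opened before lock. No section says so, and the trial team may well wait. That stands: the supportable claim is that the plan permits it.

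A reader might also infer that record matching as a whole is done with the arms known. The text does not support this. Under 2.7.3, matching is how linkage, retention and viral load are determined, so the first pass falls inside the masked period on a plain reading.

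Existing controls also count. Checks every two weeks should settle many queries early, and the audit trail makes late edits traceable. They reduce the exposure, but a trail records an edit without masking the person who made it.

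The primary outcome can be called a mechanical date rule that needs no editing, and any ambiguity in its wording a matter of definition. This stands in part. Applying the rule need not change the data, but a corrected visit date, or a decision that someone was re-incarcerated or withdrew, changes its result.

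Finally, section 4.1 says this is not an effectiveness study, and the primary outcome is reported by participants who know their arm. Both are true, and both keep the point minor.

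**Conclusion.** The point holds as a minor gap. As written, the plan allows final query resolution, re-matching, and classification of outcomes and exclusions while assignments are known and the database is open to change. This rests on two things: the inferred order of collection and lock, and the absence of any text carrying masking through to lock. The exposure is limited to final cleaning and derivation.

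On size, only the weight of a single participant can be stated: 1.7 or 0.8 percentage points on full arms, and 2.1 or 1.1 at 78% ascertainment. The plan gives no rate of late reclassification, so neither the amount nor the direction of any bias follows.

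A reader might go further and use the plan's 0.25 versus 0.49 to argue that a few changes would overturn the primary result. The documents do not support that. Section 4.1 gives those rates for being in care with an undetectable viral load, whereas the primary outcome in 2.9.2 is self-reported care. The 78% denominators also differ from the all-randomized analysis.

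**What to change.** - **Section 2.4.2:** end the masking of outcome assessors and investigators when the clean file form is signed and the database is locked, instead of when collection ends.
- **Section 5.3.3:** state that outcome and exclusion classifications are finalized before lock, from an extract without the arm variable and without the TCAC-only forms (RK003 and TR001 in Table 5). Supply TCAC visits to that extract only as dated care visits.

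The cost is two sentences and one masked extract, and investigators see the arms slightly later. Sample size, procedures and participant burden do not change.

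The change has limits. It does not remove bias from self-report by unmasked participants. It cannot mask source clinic records, which may show TCAC attendance because each TCAC reports visits to its affiliated clinic (2.8.2). Nor can it mask data-entry staff who handle the TCAC-only forms.

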### 5.3.4 Data security

All paper study records (e.g. consent forms, screening logs) will be kept in a secure location accessible only to authorized study staff, investigators, and monitors. All CRFs will be identified with study ID numbers and will not contain personnel identifiers.

### 5.3.5 Study limitations

The proposed implementation research has the following limitations:

- The study depends on contact with incarcerated individuals following release. Such individuals may be more likely to come from unstable living situations and may be highly mobile, making follow up a challenge. However, our experience is that released offenders seek re-integration services and are required to provide accurate contact information for the purposes of compliance with parole. Thus we anticipate tracing a high percentage of released offenders.
- Participant self-report regarding lapses in medications and entry into care may introduce bias as participants may favour the most socially acceptable responses. Verification of self-reported entry-into-care using clinic records will be conducted, where possible, for all participants. Data abstraction forms will be submitted to health staff at the health centres

where participants will report to have linked (refer to out-of-correctional facility clinic data abstraction form).

- Follow up and observation of participants in the pre-intervention period (more frequent than current standard of care) may result in modified or improved participant outcomes because of the fact that they are being studied.
- Pre/post assessments that we intend to apply in this study are susceptible to secular trends and to differences in outcome ascertainment. We believe that secular trends in HIV care both in DCS centers and in the public sector will be minimal in terms of HIV care in correctional centers, care in the community, and the offender population. To account for potential population differences we will include disease state and personal characteristics in the logistic regression analysis.
- A low proportion participating would markedly reduce the generalizability of the results (pre and post-intervention). Our experience is with an interest and willingness of inmates to participate in studies. Thus we do not anticipate this to be a significant limitation.

## **6 Protection of human participants**

---

### **6.1 Regulatory approvals**

This study will be conducted according to Good Clinical Practice (GCP) guidelines and completed in compliance with international and local human subject research guidelines. Approvals will be sought from University of the Witwatersrand Human Research Ethics Committee, Ekurhuleni Research Committee and the Johns Hopkins University IRB.

### **6.2 Risks and benefits**

- The nature of this research is focused on improving outcomes regarding a situation unique to incarcerated populations. The majority of potential benefit from research results will inform care for this vulnerable population. The risk posed by the components of this study are equal to or less than that of daily life. The primary risk will be of inadvertent disclosure of HIV status through contact with study staff after release from incarceration or participation in standard clinic care or transition community adherence clubs (TCACs) – risks present with obtaining public section HIV care in South Africa. While this risk is what is faced in public section care, it is of serious concern for the study and will be addressed through training of study staff not to indicate nature of contact to anyone except the participant or an individual that the participant specifically designates and by conducted TCAC meetings in a private space. In addition, as part of the assessment of the service delivery, at the end of participation we will ask about experiences, including inadvertent disclosure of HIV status.

- Disclosure to other TCAC members is unavoidable and intrinsically a component of the intervention. This aspect of the study will be clearly described to potential participants during the informed consent process.
- The other risk is that participants may have a delay in receiving higher level clinical services if they present to the TCAC with an acute illness. TCAC facilitators will make every effort to transport a participant to the relevant level of care (primary care clinic, hospital) based on symptom screening results. All symptom screen results and triage will be recorded and reviewed at least bi-weekly by the study team. We will be assessing for un-managed morbidity in both arms at each study follow-up (as a secondary outcome) to assess for any differences.
- All participants will be eligible for nominal compensation for contact with study staff (approximately US\$ 2-3 in airtime or data bundle). Participants in the TCAC are may benefit from added services. Whether this will truly reduce the burden of care, increase social capital, and lead to improved care continuum outcomes is the object of study.

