## 2.7.2 Ascertainment of linkage to care

Study staff will contact participants to ascertain care status and update contact information at 30, 90 and 182 days from release. Follow up will primarily be telephonic and will rely on participant self-report. The scheduled visit windows are: Day 30 (from 20-70 days), Day 90 (from 71-150 days), and Day 182 (from 151 – 245). The last contact attempt will be made on Day 246. At the Day 182 visit, participants will be asked for in-person contact that will occur either at research offices or at a site convenient to the participant. This study visit will be used to ascertain visit status, socio-demographic data, and to complete surveys on stigma, social capital, and care satisfaction. In addition, a whole blood sample (8mL) will be obtained for HIV RNA quantification (viral load) if there are no clinic obtained HIV RNA results from within 60 days or 182 days post-release. Refer to schedule of CRFs for data collection tools used at each study visit.

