**Table 4 : Sample size for TCAC evaluation**

Arm	Sample size
Care as usual	60
TCAC	120

Recruiting 120 in the TCAC arm will provide four TCACs with 12-20 participants each (assuming 40 to 66% successful transition in care to TCACs among participants in that arm). The 1:2 enrollment provides a greater population in the TCAC arm for assessing acceptability. This sample size has an 80% power with an alpha of 0.05 to identify an approximate difference in proportion meeting the primary outcome (in care with an undetectable viral load at 6 months) of 0.24 (e.g. 0.25 versus 0.49 meeting the primary outcome) assuming successful outcome ascertainment for 78% of participants (our success in a prior study) (Figure 2). We note that this is not an effectiveness study and we present these calculations purely to illustrate the power.

[figure not shown]

Figure 2: Proportions in care in CAU and TCAC that study is powered to detect with alpha of 0.05

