## 6.7 Data safety and monitoring

A data safety and monitoring board will be established to review of the protocol and monitoring plan prior to commencement of enrollment into the RCT and meet virtually prior to commencing enrollment and then every 6 months to review of RCT progress, enrollment and outcomes data, and any potential adverse outcomes. The meetings will review safety to suggest procedural changes and study modifications. There will be no criteria for study termination based on effectiveness because this is a pilot feasibility study with a total sample size that may not allow clear assessment of difference. The DSMB will include 3-5 members including individuals with experience with corrections research, the corrections environment, and good clinical practice.

[figure not shown]

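### Inadvertent HIV disclosure, the named primary risk, is solicited only at the end of participation, so about 40 to 45 of 180 would not be asked and a month-6 DSMB review would have almost no answers

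*Combined protocol and SAP*

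**What the plan says.** Section 6.2 states: "The primary risk will be of inadvertent disclosure of HIV status through contact with study staff after release from incarceration". The sentence goes on to include standard clinic care and TCAC participation, so both arms are exposed. Section 6.3 again ranks breach of confidentiality as the greatest risk. The enquiry into it is placed within the assessment of service delivery: "at the end of participation we will ask about experiences, including inadvertent disclosure of HIV status".

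The other risk in Section 6.2 is followed more closely: "We will be assessing for un-managed morbidity in both arms at each study follow-up". Section 6.2 also says that disclosure to fellow TCAC members is inherent in the intervention and will be explained at consent.

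Regular contacts already exist. Section 2.7.2: "Study staff will contact participants to ascertain care status and update contact information at 30, 90 and 182 days from release". At Day 182 participants also "complete surveys on stigma, social capital, and care satisfaction"; disclosure is not listed. The one-line form purposes in Table 5 do not mention it either. The Off Study form is described as documenting withdrawal, loss to follow-up or end of study procedures.

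Under Section 6.7 the DSMB is to "meet virtually prior to commencing enrollment and then every 6 months to review of RCT progress". Its remit includes potential adverse outcomes, and it may suggest procedural changes. The power statement in Section 4.1 is made "assuming successful outcome ascertainment for 78% of participants", and Section 4.2.1 sets a follow-up target of at least 75%, citing prior experience.

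**The concern.** The risk recurs throughout follow-up: at each call or visit, at clinic attendance and, in the TCAC arm, at monthly sessions and at contacts after missed sessions. A single question at the end reaches only those who stayed. Someone exposed by a call or home visit may plausibly stop answering, and then the missing answers depend on the event being measured.

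Timing matters as well. A board that can suggest changes to contact procedures needs the information while participants are still exposed. The pilot is also meant to deliver procedures ready for a full trial, so its picture of the main risk should not rest mainly on those who remained in contact.

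**Working it through.** The documents give no figure for disclosure. The inputs are 180 released participants, 60 and 120 by arm, with 78% ascertainment (Section 4.1); the 75% follow-up target (Section 4.2.1); enrolment 1 week to 3 months before release (Section 2.4.1); a Day 182 window of 151 to 245 days (Section 2.7.2); and recruitment of 35 per month previously, with half of that, 17.5, now sought (Section 4.1).

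**1. Is 78% a working assumption of the plan?** Yes: it is needed to reproduce the stated 80% power. With 60 × 0.78 = 46.8 and 120 × 0.78 = 93.6, proportions 0.25 and 0.49, and two-sided alpha 0.05 (sidedness assumed):
- Pooled proportion = (11.7 + 45.9)/140.4 = 0.41.
- SE under the null = √(0.41 × 0.59 × (1/46.8 + 1/93.6)) = 0.0881.
- SE under the alternative = √(0.1875/46.8 + 0.2499/93.6) = 0.0817.
- Power = Φ((0.24 − 1.96 × 0.0881)/0.0817) = 79.5%. With all 60 and 120 ascertained it would be 88.8%.

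**2. Participants not asked at six months.**
- At 78%: 180 × 0.22 = 39.6, about 40 (13 CAU, 26 TCAC).
- At 75%: 180 × 0.25 = 45 (15 CAU, 30 TCAC).

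**3. Effect on the recorded rate.** Let p be the true proportion with an event and L the loss among those people. With 78% seen overall, the observed rate is p(1 − L)/0.78. It is too low whenever L exceeds 22% and unbiased when L equals 22%. The documents give neither p nor L. For an assumed p of 10% (18 of 180):
- L = 22% gives 14.04/140.4 = 10%.
- L = 50% gives 9/140.4 = 6.4%.
- L = 80% gives 3.6/140.4 = 2.6%.

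**4. Answers available at a month-6 DSMB meeting** (day 183 from the start of enrolment; even enrolment and a release lag spread evenly over 7 to 91 days are assumed).
- Day 182 reached: enrolment day + lag must be at most 183 − 182 = 1. The lag is at least 7, so the count is zero.
- Day 151 reached: enrolment day + lag must be at most 183 − 151 = 32. The expected count is the daily rate × 25²/(2 × 84) = rate × 3.72. The daily rates are 17.5/30.44 = 0.575 and 35/30.44 = 1.150, giving 2.1 and 4.3 people before any loss.
- Range: if every lag were 1 week, 25 × 0.575 = 14 to 25 × 1.150 = 29. If every lag were 3 months, none.

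**5. What the existing contacts would supply by the same date** (mean lag 49 days, before contact losses).
- Day 30 reached: rate × (183 − 30 − 49) = rate × 104, or 60 to 120 people.
- Day 90 reached: rate × (183 − 90 − 49) = rate × 44, or 25 to 51 people.

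**The case against.** The strongest reply is that the plan has more routes than one question, and that several tempting conclusions go further than the text.

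- A reader might infer that people who leave because of disclosure are never counted. The documents do not support this. End of participation is not defined as Day 182 and could include an exit contact. Unanticipated problems go to the Ethics Committee/IRB (Section 6.4). Up to 36 interviews, sampled to vary by transition-in-care status, explore experienced stigma (Section 2.9.3). What stands is that none of these is stated to record disclosure systematically or to reach the DSMB.
- A reader might infer that no form holds the item. Table 5 gives only one-line purposes, and the forms are not in the text available. The care satisfaction survey could carry it. The point therefore rests on the stated timing, not on form content.
- A reader might infer that the DSMB learns nothing until recruitment is over. Recruitment runs until 180 are released. At 17.5 per month, 180 enrolments take 10.3 months (313 days), and the 180th release falls near day 313 + 49 = 362, so recruitment may still be open at month 12. By day 365 about 0.575 × (365 − 182 − 49) = 77 people would have reached Day 182, about 60 of them asked at 78%, with about 103 of 180 still short of it. A month-12 review could still act. The month-6 gap is unaffected.
- A reader might infer a bias in favour of the TCAC. Both arms are exposed, and disclosure among club members is declared part of the intervention, so the direction is not established.

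The protocol also mitigates the risk through staff training, private meeting space, a confidentiality pledge and discreet language. These reduce events but do not measure them. Finally, asking by telephone could itself expose someone. That is a fair caution, although these calls already ask about HIV care.

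**Conclusion.** The concern holds as a point about timing and reporting. The risk ranked first has one stated solicited enquiry, at the end, while another risk in the same section is assessed at every follow-up. The 40 to 45 participants not asked follow directly from the protocol's own ascertainment figures, but they are missing for any reason, and nothing links their loss to disclosure. Understatement is therefore conditional and its size unknown.

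The absence of Day 182 answers at month 6 needs only the minimum one-week lag and a DSMB clock starting with enrolment; a clock starting at the pre-enrolment meeting would make that review earlier still. The figure of 2 to 4 from Day 151 also needs even enrolment and evenly spread lags. The primary objectives and planned effectiveness outcomes are not affected. This is a cheap improvement to safety monitoring.

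**What to change.** Amend Sections 6.2 and 2.7.2 so that one short item on inadvertent disclosure (whether it occurred, date, source) is asked in both arms at the Day 30, Day 90 and Day 182 contacts, and on the Off Study form when a withdrawing participant is reached. Separate expected disclosure to fellow TCAC members within sessions from disclosure to anyone else, including onward disclosure by a member. Source categories could be study contact, TCAC member or facilitator, clinic, and other.

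Name the form that carries the item and mark it as required, because Table 7 lists the follow-up forms at these visits only as needed. In Section 6.7, add cumulative counts by arm and source to each DSMB report, with the number asked as denominator.

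The cost is a minor amendment, one item on existing forms, one DSMB table line and about a minute per contact. Staff must confirm that the participant can speak privately before asking by telephone. People lost before Day 30 would still be missed, so the number never asked should be reported beside the rate.
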